12.2. Analysis and Presentation of Data

12.2.1. General

Detailed aspects of the analysis will be presented in the SAP which will be finalized prior to unblinding.

In general, for safety analyses, descriptive statistics will be tabulated by treatment group for all participants. Unless otherwise stated, all safety analyses will use the Safety Analysis population. The analysis of AEs will consider only treatment emergent AEs (TEAEs), events occurring for the first time, or worsening, during or after the first administration of IMP. The analysis will focus on participant incidence, although for TEAEs of special interest, the number of events will also be provided (i.e., ophthalmic assessments). Tables summarizing TEAEs will be displayed by preferred term and SOC. Analysis of SAEs and the categorization of AEs by severity and relationship to IMP will also be included. AEs leading to study withdrawal or deaths on-study will also be analyzed in tables and/or listings.

Treatment-emergent changes in vital signs and laboratory parameters will be presented using tabulations by group. Descriptive statistics for each parameter and/or the change from baseline at each time point will be provided. Shift tables for selected laboratory endpoints will be presented (ALT, AST, total bilirubin, hemoglobin and methemoglobin) as defined in the SAP. For endpoints measured on a categorical scale the number of participants and proportions will be provided.

Missing data will not be imputed in general, unless otherwise specified. This is a safety study, thus multiplicity adjustment related to the primary and secondary safety endpoints analyses will not be considered.

12.2.2. Subject Demographics and Baseline Characteristics

The participant disposition and demographic data (including age, weight, height and race/ethnicity) will be tabulated by group and overall for both treatment groups. Study completion, study withdrawals, exclusions and violations will be listed and the reasons for withdrawal, exclusions and violations will be listed.

Data for background and demographic variables will be listed by treatment group and participant. Descriptive statistics will be provided by treatment group.

Medical, surgical and social history, current medical conditions results of laboratory screening tests, drug tests and any other relevant baseline information (including serology results, alcohol breathalyzer test, urine drug screen, and G6PD testing and pregnancy test results) will be listed by treatment group and participant.

Previous and concomitant medication taken at any stage from 4 weeks prior to dosing and during the study period will be listed per treatment group.

12.2.3. Safety Data

All treatment emergent AE data will be summarized separately by treatment group and by MedDRA SOC, MedDRA preferred term (PT) and severity and relationship of each AE observed.

Vital signs and routine safety laboratory data of potential clinical concern (outside local laboratory normal limits) will be summarized descriptively by treatment and time point. Both absolute values and change from baseline will be presented.

Shift tables (from the local laboratory reference range) will be generated for each treatment group to show out of range changes in laboratory parameters during the Treatment Phase.

Vital signs will be tabulated by treatment group.

The QT interval corrected for heart rate will be calculated using the Fridericia formula (QTcF) ([Fridericia 1920](#)). ECG interval data (PR, QRS, (QTcF) will be presented as summary statistics. The numbers and percentages of subjects with QTcF > 450 msec and those with clinically significant findings will be presented in a table.

Investigational medicinal product dosing and exposure over time will be summarized by treatment group and provided in a listing for each participant.

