Statistical analysis:	
Safety population: All participants who received study treatment at least once will be included in the safety population. This is the primary population for safety and tolerability analysis.
 
Intention-to-Treat (ITT) population: The ITT population will consist of all

participants as they are randomized to the study. Primary and secondary ophthalmic endpoints will be analyzed by ITT population. In this non-inferiority setting, analysis based on ITT population provides supportive evidence to analyses based on Per Protocol population.

Per Protocol (PP) population: All participants who received at least 25% of the total planned dose for IMP, had at least one valid baseline and post baseline evaluation by SD-OCT and qFAF, and had no major protocol deviations will be included in the PP population. This is the primary population for the primary safety endpoint analysis and other secondary ophthalmic endpoints.

Though this is a safety study, all subjects will be analyzed in the treatment group to which they were randomized. Detailed aspects of the analysis will be presented in the statistical analysis plan (SAP), which will be finalized prior to breaking of the study blind and database lock.

In general, for safety analyses, descriptive statistics will be tabulated by treatment group for all participants. Unless otherwise stated, all safety analyses will use the Safety population. The analysis of AEs will consider only AEs occurring for the first time, or worsening, during or after the first administration of study medication. The analysis will focus on incidence of AEs in the treatment groups, although for AEs of special interest, the number of events will also be provided (i.e. ophthalmic assessments). Tables summarizing AEs will be displayed by preferred term and system organ class (SOC). Analysis of Serious Adverse Events (SAEs) and the categorization of AEs by severity and relationship to study medication will also be included. AEs leading to study withdrawal or deaths on-study will also be presented in tables and/or listings.

Treatment-emergent changes in vital signs and laboratory parameters will be presented using tabulations by group. Descriptive statistics for each parameter and/or the change from baseline at each time point will be provided. For endpoints measured on a categorical scale the number of participants and percentages will be provided.

Primary Endpoint Measures

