2.2.3. Nonclinical Toxicology

The key target tissue effects in repeat dose toxicology studies of tafenoquine of up to 26 and 52 weeks duration in rats and dogs, respectively, were oxidative changes in red cell elements of blood (methemoglobinemia, Heinz bodies, decreased hemoglobin concentration) and findings indicative of phospholipidosis (foamy macrophage accumulation, lamellar inclusion bodies in alveolar macrophages and type II pneumocytes, and eosinophilic material in alveoli), which were manifested principally in the lung. Hemosiderin deposition in various tissues, increased spleen weight and bone marrow hyperplasia were associated with the RBC effects. A renal tubular lesion in mice and rats may have been a consequence of hemoglobin reabsorption and breakdown. There were no significant renal changes observed in the dog, with only slight pigment deposition noted. Hepatic findings (including increased weight, small increases in plasma enzyme markers, subacute inflammation and fatty changes) may reflect pathophysiological responses to either or both anemia or altered phospholipid accumulation. All of the principal pathological changes were fully reversible, or showed partial reversibility, following a 13-week drug-free recovery period in the 13-week studies.

Based on the phospholipidosis-related changes in the lungs, the approximate overall no effect dose was 0.5 mg/kg/day (26 weeks) in rats and 0.1 mg/kg/day (52 weeks) in dogs. Findings increased in severity with both dose and duration of tafenoquine administration, thereby reducing the no effect dose to lower doses in the repeat dose toxicity studies conducted for shorter periods of time than 26 weeks in rats and 52 weeks in dogs. In separate 8-week toxicokinetic studies using the same doses as the repeat dose studies, the no effect dose was shown to be associated with plasma area under the concentration-time curve from 0 to one week ($\text{AUC}_{0-1 \text{ week}}$) values of 6.66 $\mu\text{g}\cdot\text{h/mL}$ in rats and 6.84 $\mu\text{g}\cdot\text{h/mL}$ in dogs (sexes combined).

No ophthalmological changes have been observed in any of the nonclinical animal toxicity studies.

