4.2. Secondary Objectives

To assess the long-term safety and tolerability of tafenoquine versus placebo as assessed by clinical monitoring of vital signs, ECG, laboratory data, and reporting of AEs after 12 months of exposure.

To assess the long term safety and tolerability of tafenoquine after 12 months of exposure to tafenoquine versus placebo by measuring ophthalmic and psychiatric changes from baseline to end of study.

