9.2.2. Vital Signs

Vital signs including blood pressure, pulse rate, respiratory rate and sublingual body temperature after the participant has been resting for 5 minutes in a seated position as stipulated in the study schedule ([Section 1 Study Schedule of Events](#)).

The vital signs' normal ranges will be defined by site.

9.2.3. 12-lead ECG

Standard, 12-lead ECGs will be performed at Screening and nominal Weeks 4, 52, and 64. The clocks on all ECG machines will be synchronized with the central clock on a daily basis. Participants will rest for at least 5 minutes prior to the start of recording. ECG tracings will be retained and labeled as per SOPs at each clinical site.

Real-time interpretation of the tracings will be made on-site with special attention being given to changes in PR-, QRS- and QT-intervals as well as T-wave morphology changes and dysrhythmias. The QTc interval corrected for heart rate using the Fridericia formula [$QTcF = QT/RR^{(1/3)}$] ([Fridericia 1920](#)) will be calculated. Any change > 450 msec will be considered clinically significant. Any clinically significant findings will be discussed with the LMM and sponsor. The investigator will sign and date each ECG as evidence of their review.

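### Section 12.2.3 confines the by-visit laboratory summary to out-of-range results, in conflict with Sections 12.2.1 and 12.2.3.2, and a table built to that wording would misstate the tafenoquine–placebo contrast

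*Combined protocol and SAP*

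**What the plan says.** Section 12.2.3 states that "routine safety laboratory data of potential clinical concern (outside local laboratory normal limits) will be summarized descriptively by treatment and time point". The next sentence adds: "Both absolute values and change from baseline will be presented". The same section then provides shift tables against the local reference range for the Treatment Phase.

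Other current text carries no such restriction:

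- Section 12.2.1: "In general, for safety analyses, descriptive statistics will be tabulated by treatment group for all participants". It continues: "Treatment-emergent changes in vital signs and laboratory parameters will be presented using tabulations by group", and "Descriptive statistics for each parameter and/or the change from baseline at each time point will be provided". It also names ALT, AST, total bilirubin, haemoglobin and methaemoglobin for shift tables. The synopsis has the same tabulation rule.
- Section 12.2.3.2 and the secondary-endpoint text of the synopsis: laboratory parameters are summarised descriptively. Section 12.2.3.2 specifies this by treatment group and visit; the synopsis runs to Week 64.

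The secondary objective in Section 4.2 is comparative: "To assess the long-term safety and tolerability of tafenoquine versus placebo as assessed by clinical monitoring of vital signs, ECG, laboratory data". Section 2.2.3 lists among the key findings in animals "oxidative changes in red cell elements of blood (methemoglobinemia, Heinz bodies, decreased hemoglobin concentration"). Section 2.3.2 lists methaemoglobinaemia among the undesirable effects in humans.

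Section 12.2.3.2 gives BCVA, SD-OCT and LSEQ changes a mixed model with a treatment difference and 95% CI. It specifies no such estimate for any laboratory parameter.

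**The concern.** The mean of values chosen because they are abnormal is not an estimate of the average effect. Low and high results are averaged together. A different set of people enters at each visit and in each arm, so the comparison is no longer between randomised groups. The table can exaggerate a shift (two-sided limits) or nearly hide one (upper limit only).

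The wording matters because Section 12.2.3 is the specific section on safety data, whereas Section 12.2.1 speaks in general terms. The restricted rule is also the only one that promises both values and changes. A programmer could reasonably follow it.

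Shift tables do not fill the gap, because they count crossings of a limit. Section 6.2 excludes people with methaemoglobin above 2% at screening, and Section 10.11.1 makes it an event of special interest only above 10%. A general drift in that parameter, or a fall in haemoglobin within the reference range, shows up only in summaries of all participants.

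**Working it through.** **Plan's own figure.** The plan states no precision or power for laboratory data, so there is nothing to reproduce. Its 86% power concerns the primary endpoint and does not bear on this point.

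**Step 1. The passages side by side.**

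| Place | Who enters | What is shown |
|---|---|---|
| 12.2.3 | Results outside local limits | Values and changes, by arm and time point |
| 12.2.1 | All participants, in general | Each parameter and/or its change, each time point |
| 12.2.3.2 | No restriction stated | Descriptive summary, by arm and visit |
| Synopsis | No restriction stated | Same tabulation rule as 12.2.1; descriptive summary to Week 64 |

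These rules give different tables, and no sentence ranks them.

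**Step 2. What the literal 12.2.3 table would show.** Let a parameter at a visit be normal with mean μ and SD σ in an arm, with limits L and U. Put a = (L − μ)/σ and b = (U − μ)/σ. Then:

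- share out of range: P = Φ(a) + 1 − Φ(b)
- mean among those out of range: μ + σ[φ(b) − φ(a)]/P
- with equal SDs at both times, correlation ρ with Day 1 and true shift d: apparent difference in change = d + (1 − ρ)(apparent difference in level − d)

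All haemoglobin inputs below are assumptions (ρ = 0.8, d = -3 g/L). Only the 300 per arm comes from the plan (Section 5.6).

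*Scenario A: placebo mean 145, SD 10, limits 130 to 165 g/L.*

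- Placebo: a = -1.5, b = 2.0; P = 0.0668 + 0.0228 = 0.0896 (about 27 of 300); out-of-range mean 136.57.
- Tafenoquine (mean 142): a = -1.2, b = 2.3; P = 0.1151 + 0.0107 = 0.1258 (about 38 of 300); out-of-range mean 128.82.
- Apparent difference in level: 128.82 − 136.57 = -7.75.
- Apparent difference in change: -3 + 0.2 × (-7.75 + 3) = -3.95.

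*Scenario B: placebo mean 140, SD 12, limits 120 to 160 g/L.*

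- Placebo: P = 0.0478 + 0.0478 = 0.0956 (about 29 of 300); out-of-range mean 140.00.
- Tafenoquine (mean 137): P = 0.0783 + 0.0276 = 0.1059 (about 32 of 300); out-of-range mean 127.63.
- Apparent difference in level: 127.63 − 140.00 = -12.37.
- Apparent difference in change: -3 + 0.2 × (-12.37 + 3) = -4.87.

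**Step 3. The same in SD units, limits at ±1.96 SD.** About 15 of 300 placebo participants enter at each visit. True shifts of -0.1, -0.3 and -0.5 SD appear as -0.55, -1.45 and -1.99 SD in level. With an upper limit only, true shifts of +0.3 and +0.5 SD appear as +0.04 and +0.07 SD. The direction of the distortion therefore depends on the parameter.

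**Step 4. What all values would give.** With 300 per arm, the 95% CI half-width for a mean difference is 1.96 × SD × √(2/300) = 0.16 SD. For an assumed SD of change of 6, 8 or 10 g/L this is 0.96, 1.28 or 1.60 g/L, before any gain from baseline adjustment and before any loss from missing data.

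**The case against.** The strongest reply is that this is one loose phrase in a plan that is otherwise clear. Sections 12.2.1 and 12.2.3.2 and the synopsis all describe laboratory summaries by arm without an out-of-range filter. In a 1:1 randomised trial, arm means of either values or changes show the average contrast, so the and/or wording loses little. Out-of-range results have their own shift tables, and descriptive reporting of routine laboratory data is a legitimate choice. Section 12 also defers detail to an SAP to be finalised before unblinding.

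Much of this stands. A reader might infer that out-of-range results are all that is ever summarised, and that the average effect on haemoglobin and methaemoglobin is never estimated. The documents do not support that, because the unrestricted summaries would show arm means. A reader might also extend the filter to vital signs, whose "normal ranges will be defined by site" under Section 9.2.2. That is not supported either: the parenthesis concerns laboratory limits, and Section 12.2.3 separately tabulates vital signs by group.

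Nor should the red-cell rationale be pushed too far. The quoted toxicology is from animals and names phospholipidosis as well. In humans, Section 2.3.2 ties haemolytic anaemia to G6PD deficiency, which this trial excludes.

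What the reply does not remove is a specific rule that yields a misleading table, with nothing to say that the general text overrides it.

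**Conclusion.** The point holds as a conflict of wording with a real consequence if Section 12.2.3 is followed. It is not a missing analysis of the average effect. Under the assumed haemoglobin inputs, the literal table would turn a true -3 g/L into about -4 to -5 g/L in change and -8 to -12 g/L in level. For a parameter with only an upper limit, it would shrink a true shift to almost nothing. These sizes rest on normality, a correlation of 0.8 and one common pair of limits. Other inputs would change the figures but not the selection on outcome that causes the distortion.

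Separately, no between-arm laboratory difference with a confidence interval is specified, although the objective is a comparison with placebo. Leaving that descriptive is defensible, but an interval for the two red-cell parameters would serve the objective better. The primary endpoint, the sample size and data collection are unaffected.

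**What to change.** 1. In Section 12.2.3, remove the restriction to data of potential clinical concern outside local limits from the summary rule. State that all values and all changes from baseline are summarised by arm and visit through Week 64, for all participants with data.
2. In Section 12.2.1, replace the and/or with a commitment to both.
3. Report out-of-range results separately, as counts by arm and visit and in the planned shift tables.
4. For haemoglobin and methaemoglobin, add the tafenoquine-minus-placebo mean difference with 95% CI at each post-baseline visit, adjusted for the Day 1 value and labelled as a descriptive estimate.

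The cost is a wording change and two standard models, which can go into the SAP before unblinding. Two parameters at five visits (Weeks 4, 12, 24, 52 and 64) give ten more intervals. Section 12.2.1 plans no multiplicity adjustment, so an isolated interval that excludes zero should not be over-read. No new samples or visits are needed.

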In the *in vitro* human ether-a-go-go related gene (hERG) channel electrophysiology assay, the 50% maximal inhibitory concentration (IC₅₀) value for inhibition of hERG tail current was 1.1 μ M (equivalent to 0.510 μ g/mL), a relatively low micromolar value and approximately equivalent to the predicted plasma concentration at the maximum proposed dose in humans. However, there were no adverse effects observed in the ECG evaluations (including QTc interval) conducted in *in vivo* oral and IV cardiovascular and pulmonary safety pharmacology studies in dogs, and in repeat dose oral toxicity studies in dogs of up to 52 weeks in duration, in which plasma tafenoquine concentrations of ~18.4 μ g/mL and greater were achieved. In addition, there were no remarkable effects on action potential parameters in an *in vitro* dog isolated Purkinje fiber assay at concentrations up to 10 μ M. Therefore, tafenoquine has a low potential for QTc prolongation, which is supported by thorough QT/QTc clinical investigations (Green 2014).

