10. Urine drug screen positive for cocaine, methamphetamine, amphetamines, methamphetamines, barbiturates, benzodiazepines, methadone, opiates, phencyclidine, or tetrahydrocannabinols. Note urine drug screen positive for tricyclic antidepressants or benzodiazepines is allowed if participant reports prescription use for a stable medical/psychiatric condition. Limited use of prescription or non-prescription medications containing codeine and not believed to affect participant safety or the overall results of the study, may be permitted on a case-by-case basis following approval by the Investigator (in consultation with the Medical Monitor, as appropriate).
11. Blood alcohol level > 0.0 determined using an alcohol breathalyzer. Note on interviewing the participant, the investigator may allow enrolment if they are satisfied the participant does not have alcohol dependence and can successfully complete the study protocol. A second blood alcohol test level > 0.0 at Week 1, Day 1 (Visit 2) would constitute grounds for exclusion of the participant.
12. Participants with medical history that might compromise their ability to comply with the protocol.
13. History of cancer (excluding basal or squamous cell carcinomas).
14. Have a clinically significant ECG as determined by the investigator or QTc interval corrected for heart rate using the Fridericia formula ($QTcF$) > 450 msec.
15. Hemoglobin, platelet counts or neutrophil counts outside the local laboratory reference range and are judged by the investigator to be clinically significant. A laboratory test may be repeated once during screening at the discretion of the Investigator. A subject with a hematology result outside the local laboratory reference range may be admitted to the study if the result is judged as not clinically significant.
16. Alanine aminotransferase (ALT), aspartate aminotransferase (AST), total or direct bilirubin, gamma glutamyl transferase (GGT) or creatinine > 1.5 times the upper limit of normal (ULN) and are judged by the investigator to be clinically significant. A laboratory test may be repeated once during screening at the discretion of the. If other biochemistry tests fall outside the local laboratory reference range, the subject may be admitted to the study if the out-of-range result is judged as not clinically significant by the investigator.

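### ECG intervals get no stated change from baseline, visit split or tafenoquine-minus-placebo estimate, although the objective is a comparison with placebo and a Screening ECG is collected

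*Combined protocol and SAP*

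**What the plan says.** The first secondary objective (Section 4.2) is comparative and names ECG: "tafenoquine versus placebo as assessed by clinical monitoring of vital signs, ECG, laboratory data". ECG is also in the first secondary endpoint (Synopsis; Section 5.2.2). Recordings are made at Screening and at Weeks 4, 52 and 64 (Sections 1 and 9.2.3).

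Section 12.2.3 plans three ECG outputs:

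- For the intervals: "ECG interval data (PR, QRS, (QTcF) will be presented as summary statistics".
- For categories: "The numbers and percentages of subjects with QTcF > 450 msec and those with clinically significant findings will be presented in a table". This sentence covers two counts.

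The same section treats vital signs and laboratory data differently. They are summarised by treatment and time point, and "Both absolute values and change from baseline will be presented". Section 12.2.1 repeats the pattern: "Treatment-emergent changes in vital signs and laboratory parameters will be presented using tabulations by group". It then promises descriptive statistics of values or changes at each time point for those same parameters. ECG is not named.

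The by-arm layout for ECG rests on the general rule in Section 12.2.1: "In general, for safety analyses, descriptive statistics will be tabulated by treatment group for all participants".

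The by-visit summary that opens Section 12.2.3.2 lists adverse events, laboratory parameters and vital signs, and leaves ECG out. The mixed model in that section covers BCVA, SD-OCT and LSEQ only.

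**The concern.** A secondary endpoint with a placebo-controlled objective has no planned effect estimate and no interval. The baseline that would sharpen the comparison is collected in every participant but has no stated role in the ECG analysis.

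The one QTcF-specific category is an absolute cut-off. Exclusion criterion 14 (Section 6.2) applies the same 450 msec limit at entry: "Have a clinically significant ECG as determined by the investigator or QTc interval corrected for heart rate using the Fridericia formula". Participants therefore start at or below the line, most of them probably well below, and a sizeable individual rise can leave the count unchanged. A low count in both arms could be read as stronger reassurance than it gives.

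The text also does not say whether on-treatment ECGs (Weeks 4 and 52) are kept apart from the Week 64 ECG, which is taken after the expected washout.

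**Working it through.** **Inputs from the documents.** 300 per arm (Section 5.6); entry limit of 450 msec (Section 6.2); half-life 13 to 15 days (Section 2.3.3); doses on Days 1, 2 and 3, then weekly from Day 10 (Section 5.6).

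**Assumptions, not in the documents.** QTcF mean 400 to 410 msec, SD 15 to 20 msec (10 to 20 for the comparison of means), correlation between Screening and follow-up 0.6 to 0.8, complete data. The plan gives no SD, effect size or power for QTcF, so it has no figure of its own to reproduce. Its stated 86% power concerns the primary endpoint.

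**1. How often a 30 msec individual rise crosses 450.** The share is 1 − Φ((420 − mean)/SD).

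| Mean | SD | z | Share crossing |
|---|---|---|---|
| 400 | 15 | 1.33 | 9% |
| 400 | 20 | 1.00 | 16% |
| 410 | 15 | 0.67 | 25% |
| 410 | 20 | 0.50 | 31% |

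So 69 to 91% of such rises are not counted.

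**2. The count as a between-arm comparison.** With mean 405 and SD 20, the placebo share above 450 is 1 − Φ(45/20) = 1.2%. After a uniform 5 msec shift it is 1 − Φ(40/20) = 2.3%. Fisher's exact test (two-sided 5%, 300 per arm) has about 9% power. A simulation that truncates Screening values at 450, with means 395 to 415, SD 15 to 20 and correlation 0.7, gives 0 to 24% at one visit and at most 38% over two on-treatment visits. For a 10 msec shift the ranges are 0 to 85% and 0 to 97%, so the count does better when the shift is larger and baseline QTcF is high.

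**3. What the per-arm means already show.** SE of the difference = SD × √(2/300).

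| SD | SE | 95% CI half-width | 5 msec in SEs | Power for 5 msec |
|---|---|---|---|---|
| 10 | 0.82 | 1.6 | 6.1 | >99% |
| 15 | 1.22 | 2.4 | 4.1 | 98% |
| 20 | 1.63 | 3.2 | 3.1 | 86% |

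A 5 msec shift is 3 to 6 SEs and a 10 msec shift 6 to 12. A reader could see it, and could compute the difference if n, mean and SD are tabulated by arm and visit. With 240 per arm and SD 20, power for 5 msec is 78%.

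**4. What baseline adjustment adds.** The SE is multiplied by √(1 − r²). With SD 20 and r = 0.7, √(1 − 0.49) = 0.714, and the half-width is 3.20 × 0.714 = 2.3 msec. Power for 5 msec rises from 86% to 99%. Over r = 0.6 to 0.8 the half-width is 2.6 to 1.9 msec, equivalent to 1/(1 − r²) = 1.6 to 2.8 times the sample.

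**5. Week 4 against Week 52.** Assume one-compartment decay. Just after the Day 24 dose, the doses are 23, 22, 21, 14, 7 and 0 days old. The level, in units of one dose, is the sum of 2^(−age/half-life), and steady state is 1/(1 − 2^(−7/half-life)).

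- Half-life 13 days: 3.09/3.21 = 96%.
- Half-life 15 days: 3.33/3.62 = 92%.

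On drug level, Week 4 is about as informative as Week 52.

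**The case against.** The strongest reply is that little is lost. Per-arm QTcF summaries follow from the general rule in Section 12.2.1, and step 3 shows that a 5 to 10 msec mean shift would be visible in them. A reader might infer that such a shift would go unseen, or that the plan cannot show the ECG effect against placebo at all. The documents support neither. Nor is the 450 msec count the only categorical output: clinically significant findings are also tabulated, tracings are read on site with attention to interval changes (Section 9.2.3), and clinically significant changes are captured as adverse events (Section 10.11.1).

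A reader might also build a safety alarm on Section 2.2.1, where the hERG IC50 is "approximately equivalent to the predicted plasma concentration at the maximum proposed dose in humans". The same paragraph reports no adverse ECG effects in dogs dosed for up to 52 weeks at about 18.4 µg/mL and above, some 36 times the 0.510 µg/mL IC50 (18.4/0.510). It concludes that the potential for QTc prolongation is low, citing clinical QT studies. Accumulation under weekly dosing does not single out Week 52 either, because the loading doses bring Week 4 close to steady state.

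Two further points are fair. Section 12 defers detail to a SAP, so silence on visits does not mean that visits will be pooled. Laboratory and vital-sign data also get no treatment difference or interval, so a model for ECG goes beyond the plan's habit for routine safety data.

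What survives is narrower. Change from baseline and a time-point split are written down for the two companion data types and not for ECG. The comparative objective has no pre-specified ECG estimate.

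**Conclusion.** The point holds as an improvement in precision and completeness. It is neither a hidden-risk finding nor a threat to the primary analysis. By the standard that Section 12.2.3 sets for vital signs and laboratory data, ECG lacks change from baseline and a visit split. For an objective stated against placebo, it also lacks a planned difference with a confidence interval.

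The count above 450 msec does not fill the gap: it misses 69 to 91% of 30 msec individual rises, and has about 9% power for a 5 msec shift at mean 405 and SD 20. Using the Screening value would cut the 95% CI half-width from about 3.2 to 2.3 msec at SD 20 and r = 0.7.

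All QTcF means, SDs and correlations are assumptions. The gap in the text does not depend on them; the size of the gain does.

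**What to change.** Replace the ECG sentences in Section 12.2.3, and carry the change into the SAP before unblinding, with:

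> PR, QRS and QTcF, and their change from the Screening ECG, will be summarised by treatment group and visit (Weeks 4, 52 and 64). The tafenoquine-minus-placebo difference at Weeks 4 and 52 will be estimated with a 95% CI from a linear model adjusted for the Screening value and site. The number and percentage with QTcF > 450 msec will be shown by group, separately for on-treatment visits and Week 64.

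Keep the table of clinically significant findings. Site belongs in the model because it is the randomisation variable (Section 7.4). Screening is the natural baseline because no ECG is scheduled on Day 1. Categories of individual increase are not proposed, because the documents give no source for cut-offs.

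In the same edit, reconcile the endpoint's time span, which runs to Week 64 in the Synopsis and to Week 52 in Section 5.2.2.

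The cost is wording and minor programming. No new ECGs or visits are needed.
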